3.4 Dose Modifications

NOTE: Patients who interrupt trametinib for > 2 weeks will be removed from this subprotocol, unless the interruption was for reduction in LVEF, visual changes or RPED with subsequent recovery as described in corresponding tables below.

All toxicity grades below are described using the NCI Common Terminology Criteria for Adverse Events (CTCAE) version 4.0.

All appropriate treatment areas should have access to a copy of the CTCAE version 4.0. A copy of the CTCAE version 4.0 can be downloaded from the CTEP website (<http://ctep.cancer.gov>).

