3.4.3.1 Left Ventricular Ejection Fraction (LVEF)

Decreases of the left-ventricular-ejection-fraction (LVEF) have been observed in subjects receiving trametinib. Therefore, ECHOs (preferred) or MUGA's must be performed to assess cardiac ejection fraction. The procedure performed at baseline must be performed at all subsequent visits as outlined in the Time and Events Table (See Section 4.1). Electronic copies of all ECHO/MUGA scans will be collected by GSK for review. Instructions for submission of ECHO/MUGA scans are provided in the Study Procedures Manual (SPM).

Dose modification guidance and stopping criteria for LVEF decrease are provided (Table 2).

Rev. 8/15

Table 2 Dose Modification Guidelines and Stopping Criteria for LVEF Decrease

Clinic	LVEF-drop (%) or CTCAE grade	Action and Dose Modification
Asymptomatic	Absolute decrease of > 10% in LVEF compared to baseline and ejection fraction below the institution's LLN	
 Interrupt trametinib and repeat ECHO/MUGA within 2 weeks.^a If the LVEF recovers within 4 weeks (defined as LVEF ≥LLN and absolute decrease ≤10% compared to baseline): 
 Consult with the subprotocol Study Chair and request approval for restart. Restart treatment with trametinib at reduced dose by one dose level.^b Repeat ECHO/MUGA 2, 4, 8, and 12 weeks after re-start; continue in intervals of 12 weeks thereafter. If LVEF does not recover within 4 weeks: 
 Consult with cardiologist. Permanently discontinue trametinib. Report as SAE Repeat ECHO/MUGA after 2, 4, 8, 12, and 16 weeks or until resolution. 
Consult with the subprotocol Study Chair.^c

Symptomatic ^a	Grade 3: resting LVEF 39-20% or > 20% absolute reduction from baseline	
 Permanently discontinue trametinib. Report as SAE Consult with cardiologist Repeat ECHO/MUGA after 2, 4, 8, 12, and 16 weeks or until resolution
	Grade 4: resting LVEF < 20%	

Rev. Add13

Abbreviations: CTCAE = Common Terminology Criteria for Adverse Events; ECHO = echocardiogram; GSK = GlaxoSmithKline; LLN = lower limit of normal; LVEF = left ventricular ejection fraction; MUGA=Multi-gated acquisition

- If ECHO/MUGA does not show LVEF recovery after 2 weeks, repeat ECHO/MUGA 2 weeks later.

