3.4.4 Guidelines for Visual Changes

Trametinib is known to be associated with visual adverse events. An ophthalmologist should be consulted if changes in vision develop. However, if the visual changes are clearly unrelated to study treatment (e.g., allergic conjunctivitis), then monitor closely as it may be reasonable to defer ophthalmic examination. Special attention should be given to retinal findings (e.g., retinal pigment epithelial detachment (RPED) or retinovascular abnormalities (i.e., branch or central retinal vein occlusions [RVO]).

The ophthalmology exam will include best corrected visual acuity, visual field examination, tonometry, slit lamp biomicroscopic examination, and indirect fundoscopy. Optical coherence tomography is recommended at scheduled visits and if retinal abnormalities are suspected. Other types of ancillary testing including visual field examination, fundus photography, and fluorescein angiography may also be indicated as determined by clinical exam.

Guidelines regarding event management and dose reduction for visual changes considered to be related to study treatment are provided in Tables 4 and 5.

Table 4 Management and Dose Modification Guidelines for Visual Changes and/or Ophthalmic Examination Findings

CTCAE Grade ^{a,c}	Adverse Event Management	Action and Dose Modification
Grade 1 ^b	
 Consult ophthalmologist within 7 days of onset 	
 If dilated fundus examination cannot be performed within 7 days of onset, interrupt trametinib until RPED and RVO can be excluded by retina specialist/ophthalmologist. If RPED and RVO excluded, continue/or restart trametinib at same dose level If RPED suspected or diagnosed: see RPED dose modification table below (following this table); report as SAE. If RVO diagnosed: Permanently discontinue trametinib and report as SAE.
Grade 2 and Grade 3	
 Consult ophthalmologist immediately 	
 Hold trametinib If RPED and RVO excluded, restart trametinib at same dose level after visual AE is ≤ grade 1. If no recovery within 4 weeks, discontinue trametinib If RPED diagnosed, see RPED dose modification table below; report as SAE. If RVO diagnosed: Permanently discontinue trametinib and report as SAE

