Grade 4	
 Consult ophthalmologist immediately Report as SAE 	
 Hold trametinib If RPED and RVO excluded, may restart trametinib at same or reduced dose after discussion with the subprotocol Study Chair. If RVO or RPED diagnosed, permanently discontinue trametinib

Rev. 8/15

Abbreviations: RPED = retinal pigment epithelial detachment; CTCAE = Common Terminology Criteria for Adverse Events;

RVO= retinal vein occlusion; SAE = serious adverse event

a. Refers to CTCAE Version 4.0 'Eye disorders – Other, specify'

b. If visual changes are clearly unrelated to study treatment (e.g., allergic conjunctivitis), monitor closely but ophthalmic examination is not required.

c. Refers to CTCAE Version 4.0 'Retinopathy'

Table 5 Recommended dose modifications for trametinib for retinal pigment epithelial detachments (RPED)^a

CTCAE Grade	Action and Dose Modification
Grade 1 RPED (Asymptomatic; clinical or diagnostic observations only)	
 Continue treatment with retinal evaluation monthly until resolution. If RPED worsens follow instructions below
Grade 2-3 RPED (Symptomatic with mild to moderate decrease in visual acuity; limiting instrumental ADL)	
 Interrupt trametinib Retinal evaluation monthly If improved to ≤ Grade 1, restart trametinib at lower dose (reduced by 0.5 mg) or discontinue in patients taking trametinib 1 mg daily If no recovery within 4 weeks, permanently discontinue trametinib

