Grade 1	
 Initiate prophylactic and symptomatic treatment measures^a Use moderate strength topical steroid^b Reassess after 2 weeks 	
 Continue study treatment If rash does not recover to baseline within 2 weeks despite best supportive care, reduce trametinib by one dose level^c
Grade 2	
 Initiate prophylactic and symptomatic treatment measures Use moderate strength topical steroid^b Reassess after 2 weeks 	
 Reduce trametinib by one dose level 
 If rash recovers to \leq grade 1 within 2 weeks, increase dose to previous dose level If no recovery to \leq grade 1 within 2 weeks, interrupt study treatment until recovery to \leq grade 1 Restart trametinib at reduced dose level^c
Grade \geq 3	
 Use moderate strength topical steroids^b PLUS oral methyl-prednisolone dose pack Consult dermatologist 	
 Interrupt trametinib until rash recovers to grade \leq 1 Restart^c trametinib reduced by one dose level^d If no recovery to grade \leq 2 within 2 weeks, permanently discontinue trametinib

Abbreviations: CTCAE = Common Terminology Criteria for Adverse Events

- a. Rash prophylaxis is recommended for the first 6 weeks of study treatment
- Rev. 2/16 b. Moderate-strength topical steroids: hydrocortisone 2.5% cream or fluticasone propionate concentration 0.05% cream
- Rev. 8/15 c. Approval of the subprotocol Study Chair is required to restart study treatment after > 2 weeks of interruption.
- d. Escalation of study treatment to previous dose level may be considered if no rash is evident 4 weeks after restarting study treatment

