3.5.5 Trametinib Dose Modification for Toxicities Not Specified in Subsequent Sections

Rev. 8/15 **Table 12 Trametinib Treatment Modification for Clinically Significant Toxicities Deemed Related to Trametinib**

(This section is not for specific AEs such as hypertension, rash, ejection fraction changes, pneumonitis, diarrhea, liver chemistry, QTc prolongation, or visual changes. Refer to other sections for these specific AEs).		
CTCAE v4 Grade	Management Guideline	Dose Modification
Grade 1	Monitor as clinically indicated. Provide supportive care according to institutional standards.	Continue trametinib at current dose level.
Grade 2 (tolerable)		
 Interrupt treatment until resolution to grade 1 or baseline. Upon resolution, restart treatment at current dose level.
Grade 2 (intolerable) and Grade 3		
 Interrupt treatment until resolution to grade 1 or baseline. Upon resolution to baseline or grade 1, restart with one level of dose reduction. If the Grade 3 toxicity recurs, interrupt trametinib; When toxicity resolves to Grade 1 or baseline, restart trametinib reduced by another dose level.
Grade 4		
If event resolves to grade 1 or baseline discuss potential continuation of trametinib with the subprotocol Study Chair; if continuation of treatment agreed then restart trametinib at dose reduced by one dose level.
 
If event does not resolve, permanently discontinue trametinib.

Trametinib should be discontinued if treatment delay is ≥ 14 days due to toxicities. If the investigator concludes that continued trametinib will benefit a patient, the subprotocol Study Chair may be consulted for the possibility of resuming trametinib, provided that toxicities have resolved to baseline or grade 1.		

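### Section 3.4 removes patients after a trametinib hold of more than two weeks, but the rash and other-toxicity tables provide for a restart after such a hold

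*Protocol*

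**What the plan says.** **General rule.** The NOTE that opens Protocol Section 3.4 reads "Patients who interrupt trametinib for > 2 weeks will be removed from this subprotocol, unless the interruption was for reduction in LVEF, visual changes". A third exception and a condition on recovery close the list: "RPED with subsequent recovery as described in corresponding tables below". The trigger is any interruption of trametinib beyond two weeks, the consequence is removal, and three kinds of hold are excepted.

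**Tables the exceptions point to.** Each contains a four-week window:
- Table 2 (LVEF): "If the LVEF recovers within 4 weeks", the patient may restart, subject to Study Chair approval.
- Table 4 (visual changes, Grades 2 and 3): "If no recovery within 4 weeks, discontinue trametinib".
- Table 5 (RPED, Grades 2 and 3): "If no recovery within 4 weeks, permanently discontinue trametinib".

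**Rash, Section 3.5.3, Table 10 footnote c.** "Approval of the subprotocol Study Chair is required to restart study treatment after > 2 weeks of interruption". The footnote is attached to the restart steps for Grade 2 and for Grade 3 or higher. It is also attached to the Grade 1 row, where nothing is interrupted; the placement is loose, but the wording is clear.

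**Other toxicities, Section 3.5.5, Table 12 closing note.** The default is "Trametinib should be discontinued if treatment delay is ≥ 14 days due to toxicities". If the investigator sees benefit in continuing and the toxicity has resolved to baseline or Grade 1, "the subprotocol Study Chair may be consulted for the possibility of resuming trametinib".

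**The concern.** Neither rash nor the toxicities covered by Table 12 are on the NOTE's exception list, and the NOTE gives the Study Chair no power to keep a patient on treatment. Both tables nevertheless describe how a patient can resume after a hold that, under the NOTE, has already ended participation.

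These passages decide who stays on the only study drug. A site that reads the NOTE takes the patient off and has no reason to ask. A site that reads Table 10 or Table 12 may contact the Study Chair and restart. Both have followed the protocol, yet time on treatment and the recorded reason for stopping can differ between them for the same hold.

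**Working it through.** There is no planned figure to reproduce. The check sets the rules side by side for one hold length, taking 2 weeks = 14 days.

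**A hold of 21 days (21 > 14), followed by recovery**

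| Reason for hold | NOTE, Section 3.4 | Toxicity table | Agreement |
|---|---|---|---|
| LVEF, visual changes, RPED | Excepted | Tables 2, 4 and 5: within the 4-week (28-day) window | Consistent |
| Pneumonitis, Grade 2 or 3 | Removed | Table 6: discontinue if not recovered within 2 weeks | Consistent |
| Diarrhea, Grade 1 or 2 | Removed | Table 11: discontinue if the delay exceeds 14 days | Consistent |
| Rash | Removed | Table 10 footnote c: restart possible with Study Chair approval | **Conflict** |
| Other toxicity, resolved to Grade 1 or baseline | Removed | Table 12: default is to discontinue, but resumption possible after Study Chair consultation | **Conflict** |

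**Can a rash hold exceed two weeks under Table 10?** Yes, in two ways.
- Grade 2: if dose reduction does not bring recovery within two weeks, treatment is held until the rash is Grade 1 or lower. No upper limit is given.
- Grade 3 or higher: permanent discontinuation applies if the rash has not come down to Grade 2 or lower within two weeks, but restart needs Grade 1 or lower. A rash at Grade 2 after two weeks meets neither condition and stays on hold.

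These rows show how the situation arises; the contradiction itself is between footnote c and the NOTE.

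**Is Table 12 outside the exceptions?** Yes. Its header excludes ejection-fraction and visual changes, among other events, so it covers toxicities the NOTE does not exempt.

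**A hold of exactly 14 days.** The NOTE requires more than 14 days and does not trigger; Table 12 requires 14 days or more and does.

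**Routes without a time limit.** Table 7 (liver) permits rechallenge with Study Chair approval, and Table 8 footnote B (QTc) permits resumption if the investigator and the Study Chair agree. Neither mentions duration, so neither contradicts the NOTE as written, but each leaves open what happens once the hold passes two weeks.

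**Scale.** The Schema gives an accrual goal of 35, so one patient handled differently is 1/35 = 2.9% of the cohort. Section 1.1.3 reports Grade 3 or 4 rash in less than 8% of 211 patients in the Phase III melanoma study. If that rate carried over, 0.08 × 35 = 2.8, so fewer than 3 patients would be expected to have it. This is not the number with holds beyond two weeks, and it does not bound the Grade 2 route. The frequency of such holds cannot be derived from the protocol.

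**The case against.** The best defence is structural. The NOTE heads Section 3.4, while Tables 10 and 12 are in Section 3.5, so the NOTE could be read as a general default that the toxicity-specific tables refine. That the NOTE names tables for its own exceptions does not prove that later sections cannot add others. This reading is possible, but the text does not support it. The NOTE applies to any interruption of trametinib, its consequence is removal from the whole subprotocol, its wording is mandatory, and no passage gives the Section 3.5 tables precedence.

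A second point has more weight: Table 12 shares the NOTE's default and adds only a conditional, case-by-case exception. That makes its conflict weaker than the one for rash, where footnote c uses the NOTE's own threshold and presupposes that restart is possible. It remains a route that the NOTE does not allow.

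Third, both restart routes go through the Study Chair, which limits inconsistency. That holds among sites that ask, but not between sites that ask and sites that act on the NOTE alone. That some sites would not ask is an inference from the wording; the protocol contains no evidence of it.

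Finally, the two-week limit is not unsettled everywhere: Tables 6 and 11 agree with the NOTE in the rows shown. That is correct, and it confines the problem to Tables 10 and 12.

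**Conclusion.** The concern holds. For rash, and less sharply for the toxicities under Table 12, the protocol gives two different outcomes for the same patient after a hold of more than two weeks: mandatory removal, or a possible restart through the Study Chair. This is an internal contradiction rather than missing detail, and it should be fixed.

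Its extent in patients is unknown. The conclusion rests on the wording alone, on reading the NOTE's exceptions as a closed list, and on the absence of any stated order of precedence. No bias in a specific endpoint is claimed. The difference between more than 2 weeks and 14 days or more matters only for a hold of exactly 14 days and is secondary.

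**What to change.** Amend the wording so that the Section 3.4 NOTE, Table 10 footnote c and the Table 12 closing note give one answer for a hold of more than two weeks, and state which text governs if the general rule and a toxicity table differ. In the same amendment:
- state whether the differing day limits in the NOTE and Table 12 are intended;
- check the Study Chair routes in Table 7 and Table 8 footnote B against the NOTE, and say whether the two-week limit applies to them;
- tidy the placement of footnote c on the Grade 1 row of Table 10.

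Which rule applies is the study chair's clinical decision; this review asks only that the passages agree. The cost is a wording amendment, with no new patients or procedures.

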3.4.1 Dose Modification Guidelines for Trametinib Adverse Events of Special Interest

The dose levels for this study are provided in Table 1.

Dose Levels	Trametinib once daily
Full dose	2 mg
1 st Dose reduction	1.5 mg
2 nd Dose reduction	1.0 mg

Table 1 Dose Level Reduction Guidelines

3.4.2 If an AE resolves to grade 1 or baseline at the reduced dose level, and no additional toxicities are seen after four weeks of study treatment at the reduced dose, the dose of trametinib may be increased to the previous dose level. If a dose reduction below 1 mg once daily for trametinib is required, then trametinib will be permanently discontinued.

3.4.3 Guidelines for Cardiovascular Adverse Events

Cardiovascular adverse events have been seen in subjects receiving trametinib [4]). Guidelines for LVEF decreases and hypertension are provided below.

3.4.3.1 Left Ventricular Ejection Fraction (LVEF)

Decreases of the left-ventricular-ejection-fraction (LVEF) have been observed in subjects receiving trametinib. Therefore, ECHOs (preferred) or MUGA's must be performed to assess cardiac ejection fraction. The procedure performed at baseline must be performed at all subsequent visits as outlined in the Time and Events Table (See Section 4.1). Electronic copies of all ECHO/MUGA scans will be collected by GSK for review. Instructions for submission of ECHO/MUGA scans are provided in the Study Procedures Manual (SPM).

Dose modification guidance and stopping criteria for LVEF decrease are provided (Table 2).

Rev. 8/15

Table 2 Dose Modification Guidelines and Stopping Criteria for LVEF Decrease

Clinic	LVEF-drop (%) or CTCAE grade	Action and Dose Modification
Asymptomatic	Absolute decrease of > 10% in LVEF compared to baseline and ejection fraction below the institution's LLN	
 Interrupt trametinib and repeat ECHO/MUGA within 2 weeks.^a If the LVEF recovers within 4 weeks (defined as LVEF ≥LLN and absolute decrease ≤10% compared to baseline): 
 Consult with the subprotocol Study Chair and request approval for restart. Restart treatment with trametinib at reduced dose by one dose level.^b Repeat ECHO/MUGA 2, 4, 8, and 12 weeks after re-start; continue in intervals of 12 weeks thereafter. If LVEF does not recover within 4 weeks: 
 Consult with cardiologist. Permanently discontinue trametinib. Report as SAE Repeat ECHO/MUGA after 2, 4, 8, 12, and 16 weeks or until resolution. 
Consult with the subprotocol Study Chair.^c

Symptomatic ^a	Grade 3: resting LVEF 39-20% or > 20% absolute reduction from baseline	
 Permanently discontinue trametinib. Report as SAE Consult with cardiologist Repeat ECHO/MUGA after 2, 4, 8, 12, and 16 weeks or until resolution
	Grade 4: resting LVEF < 20%	

Rev. Add13

Abbreviations: CTCAE = Common Terminology Criteria for Adverse Events; ECHO = echocardiogram; GSK = GlaxoSmithKline; LLN = lower limit of normal; LVEF = left ventricular ejection fraction; MUGA=Multi-gated acquisition

- If ECHO/MUGA does not show LVEF recovery after 2 weeks, repeat ECHO/MUGA 2 weeks later.
- Escalation of trametinib to previous dose level can be considered if LVEF remains stable for 4 weeks after restarting of trametinib. Approval from the subprotocol Study Chair is required.
- Symptoms may include: dyspnea, orthopnea, and other signs and symptoms of pulmonary congestion and edema.

3.4.3.2 Hypertension

Increases in blood pressure (BP) have been observed in patients receiving trametinib. Recommendations for BP monitoring and management are provided below.

Monitoring: All BP assessments should be performed under the following optimal conditions:

- The subject has been seated with back support, ensuring that legs are uncrossed and flat on the floor.
- The subject is relaxed comfortably for at least 5 minutes.
- Restrictive clothing has been removed from the cuff

area, and the right cuff size has been selected.

- The subject's arm is supported so that the middle of the cuff is at heart level.
- The subject remains quiet during the measurement.
- In subjects with an initial BP reading within the hypertensive range, a second reading should be taken at least 1 minute later, with the two readings averaged to obtain a final BP measurement. The averaged value should be recorded in the eCRF.
- Persistent hypertension is defined as an increase of systolic blood pressure (SBP) >140 mmHg and/or diastolic blood pressure (DBP) >90 mmHg in three consecutive visits with blood pressure assessments from two readings as described above. Visits to monitor increased blood pressure can be scheduled independently from the per-protocol visits outlined in the study calendar. Ideally, subsequent blood pressure assessments should be performed within 1 week.

Table 3 Management and Dose Modification Guidelines for Hypertension

Management and Trametinib Dose Modification for Hypertension		
Event	Management Guideline	Dose Modification

Definitions used in the table:
 
 - Persistent hypertension: Hypertension detected in two separate readings during up to three subsequent visits. - Well-controlled hypertension: Blood pressure of SBP ≤140 mmHg and DBP ≤90 mmHg in two separate readings during up to three subsequent visits. - Symptomatic hypertension: Hypertension associated with symptoms (e.g., headache, light-headedness, vertigo, tinnitus, episodes of fainting or other symptoms indicative of hypertension) that resolve after the blood pressure is controlled within the normal range. - Asymptomatic hypertension: SBP >140 mmHg and/or DBP >90 mmHg in the absence of the above symptoms. 		

(Scenario A) Asymptomatic and persistent SBP of ≥ 140 and < 160 mmHg, or DBP ≥ 90 and < 100 mmHg, or Clinically significant increase in DBP of 20 mmHg (but still below 100 mmHg).
	
 • Adjust current or initiate new antihypertensive medication(s). • Titrate antihypertensive medication(s) during the next 2 weeks to achieve well-controlled BP. If BP is not well-controlled within 2 weeks, consider referral to a specialist and go to scenario (B). 	
Continue trametinib at the current dose.

(Scenario B) Asymptomatic SBP ≥ 160 mmHg, or DBP ≥ 100 mmHg, or Failure to achieve well-controlled BP within 2 weeks in Scenario A.
	
 • Adjust current or initiate new antihypertensive medication(s). • Titrate antihypertensive medication(s) during the next 2 weeks to achieve well-controlled BP. 	
 • Interrupt trametinib if clinically indicated. • Once BP is well-controlled, restart trametinib reduced by one dose level.^a

(Scenario C) Symptomatic hypertension or Persistent SBP ≥ 160 mmHg, or DBP ≥ 100 mmHg, despite antihypertensive medication and dose reduction of trametinib
	
 • Adjust current or initiate new antihypertensive medication(s). • Titrate antihypertensive medication(s) during the next 2 weeks to achieve well-controlled BP. • Referral to a specialist for further evaluation and follow-up is recommended. 	
 • Interrupt trametinib. • Once BP is well-controlled, restart trametinib reduced by one dose level.^a

(Scenario D) Refractory hypertension unresponsive to above interventions or hypertensive crisis.
	
Continue follow-up per protocol.
	
Permanently discontinue trametinib.

a. Escalation of trametinib to previous dose level can be considered if BPs remain well controlled for 4 weeks after restarting of trametinib. Approval from the subprotocol Study Chair is required.
		

Rev. 8/15

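### Table 3 does not say whether a blood pressure reading is a single cuff value or the visit's final BP, and the answer decides who counts as persistent or well-controlled

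*Protocol*

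**What the plan says.** All of this is in Protocol section 3.4.3.2 (Hypertension).

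- **Monitoring list, when a second reading is taken:** "In subjects with an initial BP reading within the hypertensive range, a second reading should be taken at least 1 minute later".
- **Monitoring list, what is then kept:** "with the two readings averaged to obtain a final BP measurement. The averaged value should be recorded in the eCRF". A visit therefore ends with one value.
- **Monitoring list, persistent hypertension:** pressure above 140 systolic and/or 90 diastolic "in three consecutive visits with blood pressure assessments from two readings as described above".
- **Table 3, persistent hypertension:** "Hypertension detected in two separate readings during up to three subsequent visits".
- **Table 3, well-controlled hypertension:** "Blood pressure of SBP ≤140 mmHg and DBP ≤90 mmHg in two separate readings during up to three subsequent visits".
- **Table 3, threshold:** asymptomatic hypertension is "SBP >140 mmHg and/or DBP >90 mmHg in the absence of the above symptoms".

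The terms drive actions in the scenario rows. Persistence is part of the entry to Scenario A and one of the entries to Scenario C: "Persistent SBP ≥ 160 mmHg, or DBP ≥ 100 mmHg, despite antihypertensive medication and dose reduction of trametinib". Failure to reach good control within two weeks moves a patient from A to B. Reaching good control is the condition for restarting trametinib at a reduced dose in B and C.

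**The concern.** The Monitoring list uses the word *reading* for one cuff measurement and a different term for the averaged result of the visit. Table 3 then counts readings and never refers to the final value. A visit that starts high contributes two readings and a visit that starts normal contributes one, so three visits can supply between three and six. With more than three readings available, two high and two normal ones can coexist. Two states that are meant to be opposites then stop excluding each other.

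What is at stake is reproducibility of dose decisions for a listed toxicity. One site may count cuff values and another the final visit values. With identical measurements they can disagree on whether a patient is controlled, and so on escalation from A to B and on restart. For a repeated reading the section specifies only the average for the eCRF, so a decision made on single readings cannot be checked from that entry.

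**Working it through.** The protocol gives no figure to reproduce here. The check is a worked record, a count of possible patterns and a simulation under assumed SDs.

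**1. Worked record** (systolic; diastolic taken as 90 or below throughout).

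| Visit | First | Second | Final value |
|---|---|---|---|
| 1 | 146 | 138 | (146 + 138)/2 = 142 |
| 2 | 145 | 139 | (145 + 139)/2 = 142 |

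On cuff values, 146 and 145 meet Table 3's persistent definition, and 138 and 139 meet its well-controlled definition. On final values, both visits are hypertensive and control is not met.

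**2. All possible three-visit patterns.** The Monitoring list allows four visit types: normal first reading (one reading); high then high; high then normal with a high average; high then normal with a normal average. Three visits give 4³ = 64 patterns.

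- *Cuff values.* Fewer than two high readings: three normal visits (1 pattern), or two normal visits and one mixed (3 × 2 = 6), in all 7. Fewer than two normal readings: three high-high visits (1), two high-high and one normal (3), two high-high and one mixed (3 × 2 = 6), in all 10. No pattern is in both groups, so 64 − 7 − 10 = **47 of 64** meet both definitions.
- *Cuff values that must come from different visits:* **44 of 64** meet both.
- *Final values:* **0 of 64**, because three values cannot include two high and two normal.

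These are counts of patterns, not probabilities.

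**3. Does the other definition of persistent hypertension remove the problem?** No. Add a third visit of 144 then 138, average (144 + 138)/2 = 141. All three final values are hypertensive, which meets the Monitoring list's three-visit definition. The readings 138, 139 and 138 still meet Table 3's definition of control if cuff values count. Separately, even on final values the two definitions of persistent disagree whenever exactly two of three visits are high: 3 × 2 × 2 × 2 = 24 of 64 patterns.

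**4. Size under assumptions.** The model covers systolic pressure only, with constant true pressure. Visit means are normal around it with a between-visit SD, and readings are normal around the visit mean with a within-visit SD. A second reading is used only if the first exceeds 140. There were 400,000 simulated patients per setting. Each cell gives the percentage meeting both Table 3 definitions on cuff values, then the percentage hypertensive on all three final values yet controlled on cuff values.

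| Within/between SD (assumed) | True 142 | True 145 | True 150 |
|---|---|---|---|
| 3/0 | 36; 3.3 | 2; 0.5 | 0; 0.0 |
| 5/5 | 44; 1.1 | 27; 1.3 | 5; 0.5 |
| 7/0 | 52; 2.6 | 34; 3.2 | 6; 1.0 |
| 7/8 | 46; 0.9 | 36; 1.1 | 16; 0.9 |

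Over a wider grid (within 3, 5, 7; between 0, 5, 8) the second quantity falls as low as 0.3% at 142 and 145. At true 145 with SDs 5/5, 30% are controlled on cuff values, against 20% if at least two of three final values must be 140 or below.

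**The case against.** **Table 3 never says that single cuff values are the unit.** The Monitoring list governs all BP assessments and reduces each visit to a final value. A site that reads Table 3 in that light sees no overlap. This stands. A reader might infer that the plan defines both states by single readings and so contradicts itself outright; the text does not go that far. What it does is use a word that the same section has given to the single measurement, without tying it to the final value.

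**No scenario row applies both definitions to the same visits.** A trigger comes first, then up to two weeks of titration, then control is assessed. This also stands, and it limits what the overlap percentages mean. They hold true pressure constant and score one window, which is not the Table 3 workflow. It does not remove the ambiguity, because control alone is decided differently under the two units.

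**The overlap near 140 drives few actions through persistence.** In Scenario A the dose continues unchanged. Scenario C needs 160 systolic or 100 diastolic; under the same model, two readings of at least 160 and two of at most 140 in the same three visits occur in at most 1.8%. The practical weight therefore falls on well-controlled.

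**The section presents itself as recommendations**, and interruption in Scenario B is left to clinical indication. That lowers the stakes somewhat. Restart is still tied to control.

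**Conclusion.** The point holds as an unresolved unit of count in management definitions. On cuff values the same visits can meet both definitions, and a patient can be called well-controlled while the averaged pressure is hypertensive. On final values neither can happen. The logical result needs no assumption beyond the protocol's own measurement rule.

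The size does rest on assumptions: the SDs, constant true pressure and systolic pressure only. The effect is concentrated near the cut-off and fades by a true pressure of 150. A reader might take the 36-52% overlap at true 142 as the share of patients handled wrongly; the documents do not support that, since trigger and control are assessed in sequence with treatment between. The case with the plainest harm, hypertensive on all three averages yet labelled controlled, is uncommon at about 0.5-3% for true pressures of 142-145.

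No analysis or endpoint in the protocol uses these terms. The consequence is inconsistent dose handling between sites, which is worth correcting because the correction is small.

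**What to change.** The sponsor should reconcile the Monitoring list with the Table 3 definitions so that one stated unit, either the single reading or the final visit value, governs both persistent and well-controlled hypertension. The same edit should settle the two definitions of persistent hypertension: three consecutive visits in the Monitoring list, two readings in up to three visits in Table 3. If single readings are chosen, the text should also say what applies when a record meets both definitions. This review does not choose the unit, the number of visits or any threshold or dose action; those are clinical decisions.

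The cost is one wording change. It needs no extra visit or measurement. Depending on the unit chosen, some control decisions, and so some restarts, may fall slightly earlier or later than sites now apply them.
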